5.4 Study Rationale and Purpose

Inhalation therapy is the cornerstone therapy in asthma and COPD patients. Unfortunately, many errors are associated with the use of inhalers, which leads to poor outcome for patients. Problems with the use of pressurized metered dose inhalers were described shortly after the launch of pMDI and still persist today. The use of dry powder inhalers (DPI's) is also frequently associated with errors.

The most common errors in the use of pMDI's are incorrect coordination, insufficient depth and/or speed of inspiration and no postinhalation breath-hold in.

The most frequent DPI errors are no complete expiration before inhalation, incorrect preparation and lack of postinhalation breath-hold in.

The overall prevalence of poor technique was 31%, of acceptable technique 41% and of correct technique only 31%. It can be concluded that incorrect inhaler technique in asthma and COPD patients is unacceptably frequent. Over the past 40 years, the prevalence of correct inhaler technique has not improved. The lack of correct inhalation technique may be a major obstacle, which withholds patients from achieving optimal asthma or COPD control. (7)

Incorrect use of inhalers is associated with reduced disease control. The strongest associations have been found between incorrect inhaler technique and older age, lower schooling and lack of

instruction about the correct inhaler technique by healthcare workers. These associations are independently of the inhaler type. Poor inhaler use is most common in older ages, but can occur at all ages. The misuse of inhalers is associated with an elevated risk of hospitalization, visits to the emergency department, treatments with oral corticosteroids and antimicrobials, and poor disease control. Instruction by healthcare workers about the correct use of inhalers is the only modifiable factor that can be useful to reduce the prevalence of inhaler misuse. (8)

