9.2 Inclusion Criteria

- COPD patients (GOLD II-IV)
- Patients with severe asthma included in the Belgian Severe Asthma registry aged <70
- Patients with asthma of any severity aged ≥ 70 y
- Patients with mild-to moderate asthma aged < 70y

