9.3 Exclusion Criteria

- Patients with asthma or COPD not on inhaled therapy for maintenance treatment
- Patients younger than 18y

- Patients unable to give their informed consent due to mental or physical disability
- Patients who don't speak French or Dutch

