14.4 Statistical Considerations and Data Analysis

The promotor and investigators from UZ Brussel's respiratory division will perform the statistical analysis, with the help of VUB statistician [name].

The statistical plan was discussed during a meeting with professor [name] (see below).

Sample size calculation

This is a purely explorative study, since there is no a priori hypothesis to be confirmed. Hence, no formal sample size calculation is possible.

The findings of this study could later on be confirmed and assessed more extensively in larger dedicated studies.

For this study however, it is important that the patient groups be stratified according to their occurrence in society. We believe this will be the case when the in-and exclusion criteria for this study will be applied.

Statistical analysis

Descriptive statistics will be used to describe the prevalence of patient/device mismatch for the entire study population.

The comparison of the prevalence of patient/device mismatch between patient subgroups and the comparison of the fail rates for each objective measurement separately between patient subgroups will be done by means of the Chi-square test and will be visualized in cross-tables.

To study correlations between patient characteristics (independent variables) and pass or fail rates for each of the three test criteria (dependent variables), box-plots will be used for continuous variables (for example weight and length), whereas the Chi-square test will be used for categorical variables (for example diagnosis, age expressed in years, GOLD stage and GOLD group).

15 Ethical Considerations

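### Asthma groups are banded at age 70 and COPD is not, so the crude chi-square comparisons in section 14.4 mix disease with age

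*Protocol*

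**What the plan says.** Protocol section 9.2 defines four groups. COPD enters as "COPD patients (GOLD II-IV", with no age band. Only the general exclusion in 9.3, "Patients younger than 18y", limits age. The asthma groups are all banded: "Patients with severe asthma included in the Belgian Severe Asthma registry aged <70", "Patients with asthma of any severity aged ≥ 70 y" and "Patients with mild-to moderate asthma aged < 70y". The synopsis sets the numbers at 40 COPD, 20 severe asthma, 40 asthma aged 70 or over, and 40 mild-to-moderate asthma under 70.

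Section 14.4 states that the comparison between subgroups, for mismatch and for each fail rate, "will be done by means of the Chi-square test and will be visualized in cross-tables". For patient characteristics against pass or fail, "the Chi-square test will be used for categorical variables (for example diagnosis" is the first example given. Neither comparison is adjusted for age or stratified by it.

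Two other places bear on the point. The synopsis announces a multiple regression for inability to use each of the three device classes, names no covariates, and is not taken up in 14.4. Section 7.2 plans to correlate each fail rate with patient characteristics, age among them, within each subgroup and overall.

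**The concern.** The protocol's own rationale in section 5.4 says: "The strongest associations have been found between incorrect inhaler technique and older age", along with schooling and lack of instruction. Age is thus expected to drive the outcome. It is also distributed unevenly over the groups by design: fixed by quota within asthma, left open within COPD.

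A crude COPD-versus-asthma contrast therefore carries an age component whose size and direction depend on who attends the clinic. It would change if the asthma quotas changed, even if nothing clinical did. The subgroup comparison serves a stated secondary objective, and section 14.4 expects the findings to be taken further in larger studies. An age difference read as a disease difference would point those studies the wrong way.

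**Working it through.** The protocol gives no alpha, power, effect size or expected fail rate, so there is no figure of its own to reproduce.

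**Inputs from the protocol.** Group sizes 40/20/40/40 (synopsis), total 140. Asthma total 20 + 40 + 40 = 100. With the age limits in 9.2, the asthma share aged 70 or over is 40/100 = 40%.

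**Assumptions, not in the protocol.** Fail risk depends on age only, *p*y under 70 and *p*o from 70, the same in both diseases. A share *f* of COPD patients is 70 or over. The test is two-sided at 5%.

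**Expected rates.**
- COPD: (1 − *f*)·*p*y + *f*·*p*o
- All asthma: 0.6·*p*y + 0.4·*p*o
- Mild-to-moderate asthma under 70: *p*y

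Subtracting:
- COPD minus all asthma = (*f* − 0.4)(*p*o − *p*y)
- COPD minus mild-to-moderate asthma under 70 = *f*(*p*o − *p*y)

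The first gap is zero at *f* = 0.4. The second is zero only if *f* = 0 or age has no effect.

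**Example.** Take *p*y = 15%, *p*o = 35%, *f* = 0.5. COPD is 0.5 × 15 + 0.5 × 35 = 25%. All asthma is 0.6 × 15 + 0.4 × 35 = 23%. COPD is then 2 points above all asthma, 10 points above mild-to-moderate asthma under 70 (15%) and 10 points below asthma aged 70 or over (35%), with no disease effect at all.

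**Rejection rates.** 200,000 simulated trials per row, with the number of COPD patients aged 70 or over drawn as binomial(40, *f*). The crude tests are Pearson chi-square, 40 v 100 and 40 v 40. The stratified test is Mantel-Haenszel for COPD v all asthma in two age bands, with the two under-70 asthma groups combined (20 + 40 = 60): [Σ(a − n₁m/N)]² / Σ[n₁n₂m(N − m)/(N²(N − 1))]. In each band, a is COPD fails, n₁ and n₂ the COPD and asthma numbers, m all fails, and N = n₁ + n₂.

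| *p*y / *p*o | *f* | COPD v all asthma: gap, rejection | COPD v mild-to-moderate <70: gap, rejection | Age-stratified COPD v all asthma |
|---|---|---|---|---|
| 10% / 20% | 0.3 | −1, 4.8% | 3, 7.8% | 4.8% |
| 10% / 20% | 0.5 | 1, 5.4% | 5, 11.1% | 4.9% |
| 10% / 20% | 0.7 | 3, 8.0% | 7, 15.8% | 4.9% |
| 15% / 35% | 0.3 | −2, 5.1% | 6, 10.9% | 5.0% |
| 15% / 35% | 0.5 | 2, 5.9% | 10, 20.2% | 4.9% |
| 15% / 35% | 0.7 | 6, 12.4% | 14, 32.9% | 5.0% |
| 10% / 40% | 0.3 | −3, 5.7% | 9, 21.4% | 5.0% |
| 10% / 40% | 0.5 | 3, 6.8% | 15, 43.5% | 4.9% |
| 10% / 40% | 0.7 | 9, 20.9% | 21, 66.8% | 5.0% |

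Gaps are in percentage points. At *f* = 0.4 the crude all-asthma gap is zero and the test rejects in 4.7-4.8% of trials. Outside this grid, with an older COPD group and risks of 20%/40%, the crude COPD-versus-all-asthma test rejects in 15.6% (*f* = 0.8) and 28.9% (*f* = 1).

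**The case against.** The strongest reply has four parts.

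- **A multivariable analysis is planned.** The synopsis regression concerns fitness for each device class, which is derived from the same three pass/fail tests, and its covariates may be listed in an analysis plan that is not shown. This stands in part: a reader might infer that disease and age cannot be separated at all, and the documents do not support that. Age is recorded and a regression is announced. But the regression does not cover the subgroup comparisons, and 14.4, which does fix their method, leaves age out.
- **Age is examined within subgroups (section 7.2).** True, but a correlation within COPD does not adjust a contrast between COPD and asthma.
- **The bias may be small.** This stands for the diagnosis test. In six of the nine settings, crude COPD versus all asthma rejects in under 7% of trials. A reader might attach the 8-67% range to that test, but it belongs to the single contrast with mild-to-moderate asthma under 70, which 14.4 does not single out. The like-for-like crude counterpart of the stratified 5% is the 5-21% range.
- **The chi-square is not wrong for what it tests.** If groups of different age have different fail rates, rejection is correct for the groups as defined. Three of them are defined by age on purpose, and the study is declared exploratory. This also stands: the fault lies in reading the result as a disease effect, for which the plan supplies no adjusted contrast.

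**Conclusion.** The point holds as a limit on interpretation. As 14.4 is written, a COPD-versus-asthma difference in mismatch or fail rate partly reflects age, because the asthma age mix is fixed by quota and the COPD mix is not.

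Under the stated assumptions the age component is 1-9 points for COPD versus all asthma (rejection about 5-21%) and 3-21 points for COPD versus mild-to-moderate asthma under 70 (about 8-67%). It can have either sign in the first contrast and vanishes there at a 40% COPD share. These figures rest on a COPD age mix and an age effect that the protocol does not give. They also use the under-70 limit on severe asthma from 9.2, which the synopsis does not repeat.

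The primary objective, a descriptive prevalence, does not depend on these tests. The age contrast within asthma is intended and is not at issue. The change is worth making because it is cheap and a secondary comparison cannot be read properly without it.

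**What to change.** In section 14.4:

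- Keep the crude four-group cross-table as description, and show COPD split at under 70 and 70 or over beside it.
- For mismatch and for each of the three fail criteria, add one age-adjusted contrast with a 95% confidence interval. Use either a logistic model with diagnosis and age as a continuous variable, or a Mantel-Haenszel comparison of COPD with asthma stratified at 70. The latter needs the two under-70 asthma groups combined so that each band is a 2×2 table.
- Reconcile this with the synopsis regression: carry it into 14.4 and name its outcomes and covariates, with age and diagnosis among them.

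The cost is wording only, since age and diagnosis are already collected and no extra patients or visits are needed. The downsides are wider intervals within age bands, because 40 COPD patients are split in two, and, for the Mantel-Haenszel version, an under-70 asthma comparator whose severity mix is set by the 20:40 quota.

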Endpoints:	To assess if the choice of inhaler device category differs when based on objective assessments, as compared to the choice made by the treating physician (during routine clinical practice), which is primarily based on subjective evaluation.
Study population:	Asthma and COPD patients treated with inhaled medications. Subjects will be recruited in the respiratory outpatient clinic in UZ Brussel after a scheduled consultation with their pulmonologist.
Number of patients:	40 COPD patients (GOLD II-IV); 20 patients with severe asthma, 40 patients with asthma aged ≥ 70 y, 40 patients with mild-to moderate asthma aged < 70 y
Overview of study design:	Single center, single visit cross-sectional interventional study without device or investigational product
Statistical Considerations:	Descriptive analysis will be used to describe the prevalence patient/device mismatch. Multiple regression analysis will be performed to identify patient characteristics associated with inability to use the 3 main classes of inhalation devices respectively. Due to the exploratory nature of this study, no formal power calculation can be performed.
Sponsor:	This study is an academic study and has no sponsor.
Inclusion Criteria:	
 - COPD patients (GOLD II-IV) - Patients with severe asthma - Patients with asthma aged ≥ 70y - Patients with mild-to moderate asthma aged < 70y
Exclusion Criteria:	
 - Patients with asthma or COPD not on inhaled therapy for maintenance treatment - Patients younger than 18y - Patients unable to give their informed consent due to mental or physical disability - Patients who don't speak Dutch or French
Target Date of first enrolment:	To be determined. Probably Q4 2021.

Target sample size:	No target sample size calculation could be performed due to exploratory nature of the study (please see above)
---------------------	--

2 Protocol Version History

Version No.	Release Date	Summary of Changes

3 Sponsor/Coordinating Investigator Information

Coordinating Investigator (promotor): [name]. [name]

Sponsor: NA

Principal Investigator [name]

Co-investigators: [name]. [name], [name] (co-promotor), [name], [name]

Additional co-researchers: NA

Statistician

Laboratory (ies): NA

Pharmacy: NA

Study Coordinator: [name]

Study sites and co-investigators: respiratory outpatient clinic UZ Brussel

4 List of Abbreviations

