7.2 Secondary Objectives

To assess the proportion of patient/device mismatch per patient subgroup.

To assess the fail rates for each objective measurement separately for the entire study population and per patient group.

To correlate the fail rates for each objective measurement separately with patient's characteristics per patient subgroup and overall (age, sex, height, weight, FEV₁, FVC, PIF, GOLD grade and group, smoking status, GINA treatment step, oral corticosteroid dose).

To correlate fail rates for each objective measurement with patient's characteristics.

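### Section 14.4 relates continuous characteristics to test failure by box-plot alone, so the secondary objective to correlate them yields no association measure, interval or test

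*Protocol*

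**What the plan says.** Protocol section 7.2 gives the objective: "To correlate the fail rates for each objective measurement separately with patient's characteristics per patient subgroup and overall". The list begins with age, sex, height, weight and FEV1 and continues with "FVC, PIF, GOLD grade and group, smoking status, GINA treatment step, oral corticosteroid dose".

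Protocol section 14.4 gives the method. The dependent variables are "pass or fail rates for each of the three test criteria (dependent variables"). For continuous characteristics, "box-plots will be used for continuous variables (for example weight and length"). By contrast, "the Chi-square test will be used for categorical variables (for example diagnosis, age expressed in years, GOLD stage and GOLD group"). Age in years is thus placed with the categorical variables.

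The protocol summary (section 1, statistical considerations) announces something else: "Multiple regression analysis will be performed to identify patient characteristics associated with inability to use the 3 main classes of inhalation devices respectively". Section 14.4 does not mention this regression.

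**The concern.** An objective to correlate asks how strongly a characteristic goes with failure and how sure one can be of that. Section 14.4 answers with a formal test for categorical characteristics and with a picture for continuous ones. The contrast it draws between the two makes the box-plot the method for continuous variables, not a display beside an analysis. This choice is written into the protocol, so it is not a detail left open for a later analysis plan.

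At stake is what the study can report on body size, lung function, PIF and steroid dose. A reader of the box-plots would see whether the fail and pass groups look different, but could not tell a chance difference from a real one or compare characteristics on a common scale. Section 14.4 also says that larger studies might later confirm the findings. Planning those would need an effect size with its uncertainty.

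**Working it through.** The protocol gives no alpha, power, effect size or expected fail rate, so it has no figure of its own to reproduce. Three checks were made.

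**1. How many characteristics are affected.** Section 7.2 lists age, sex, height, weight, FEV1, FVC, PIF, GOLD grade, GOLD group, smoking status, GINA step and oral steroid dose: 12 items, or 11 if GOLD grade and group count as one. Section 14.4 gives only weight and length as examples of continuous variables. FEV1, FVC, PIF and steroid dose are added here because they are measured on a continuous scale. That makes 6.

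- With age categorical, as in 14.4: 6/12 = 50% or 6/11 = 55%.
- With age continuous, against 14.4: 7/12 = 58% or 7/11 = 64%.

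**2. Whether the summary's regression covers the objective.**

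| Place | Outcome | Method for continuous characteristics |
|---|---|---|
| Section 7.2 | failure of each test | none named (objective only) |
| Section 14.4 | pass or fail on each test | box-plot |
| Protocol summary | inability to use each of three device classes | multiple regression |

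The regression's outcome is not the one in 7.2 and 14.4. Section 6.2 derives device fitness from the three test results through a diagram, so the outcomes are linked but not the same. A coefficient for device-class inability is not an estimate of the relation with failing one test.

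**3. What precision an estimate would have.** The summary's group sizes are 40 COPD patients plus "20 patients with severe asthma, 40 patients with asthma aged ≥ 70 y, 40 patients with mild-to moderate asthma aged < 70 y", so N = 40 + 20 + 40 + 40 = 140. The fail rate f is not in the protocol and is assumed to lie between 5% and 30%.

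- Half-width of the 95% CI for a fail-minus-pass difference, in SD units: 1.96 × sqrt(1/n_fail + 1/n_pass).
- Factor by which the 95% CI extends either side of an odds ratio per SD, near the null: exp(1.96 / sqrt(N × f × (1 − f))).

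Example at N = 140 and f = 5% (7 fail, 133 pass): 1.96 × sqrt(1/7 + 1/133) = 0.76 SD, and exp(1.96 / sqrt(140 × 0.05 × 0.95)) = 2.14.

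| Assumed fail rate | N = 140: half-width (SD) | N = 140: odds-ratio factor | Group of 40: half-width (SD) | Group of 20: half-width (SD) |
|---|---|---|---|---|
| 5% | 0.76 | 2.14 | 1.42 | 2.01 |
| 10% | 0.55 | 1.74 | 1.03 | 1.46 |
| 20% | 0.41 | 1.51 | 0.77 | 1.10 |
| 30% | 0.36 | 1.44 | 0.68 | 0.96 |

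In the severe asthma group of 20, the fail box would be drawn from 20 × 0.05 = 1 to 20 × 0.30 = 6 patients. An estimate is feasible in the whole population. Per subgroup it is very imprecise, and a box-plot would not reveal that.

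**The case against.** The strongest defence is that the study is exploratory, has no hypothesis to confirm, and has mismatch prevalence as its primary objective, which this point leaves untouched. Descriptive display is then a defensible, if thin, choice for a secondary objective. That lowers the weight of the point. It does not remove it, because exploratory work still needs estimates with their uncertainty, and 14.4 itself goes beyond display for the categorical variables.

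Several stronger readings are tempting and are not supported:

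- A reader might infer that continuous characteristics are analysed by box-plot throughout the protocol. The summary's regression could give estimates for them, though for device-class inability.
- A reader might infer that most of the listed characteristics are affected. On 14.4's own assignment it is exactly half, or just over half if the two GOLD items are merged.
- A reader might say that a box-plot conveys nothing about size. It shows medians and quartiles; what is missing is an association measure, an interval and a test.
- A reader might think that only continuous characteristics lack an estimate. The Chi-square test gives a p-value but no effect size or interval either.
- A reader might expect steroid dose to be zero in most patients outside severe asthma, so that its boxes collapse. The protocol does not say so; this is an assumption.

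It is also fair to object that the half-widths describe what 140 patients can support, not the harm done by a box-plot. That stands: they show only the uncertainty left undisclosed. Finally, adding estimates multiplies comparisons: 6 characteristics × 3 tests × 5 populations (overall and four subgroups) = 90. That is a reason to label them exploratory and to stress the overall population.

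**Conclusion.** The point holds within limits. For failure of each test, 14.4 fixes a graphical method for continuous characteristics that cannot deliver the objective in 7.2. This affects height, weight, FEV1, FVC, PIF and oral steroid dose, about half of the list. The regression in the summary does not repair it and leaves two parts of the protocol unaligned.

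The undisclosed uncertainty in the whole population is a half-width of 0.76 to 0.36 SD. That range rests on assumed fail rates of 5% to 30%, all 140 planned patients contributing, and a common SD in the two groups. Section 6.1 collects FEV1, FVC and PIF from the file only where available, so intervals for these could be wider. The defect concerns a secondary, exploratory objective and is worth correcting mainly because the correction is cheap.

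**What to change.** In section 14.4:

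- Keep the box-plots as display. For each continuous characteristic add a fail-minus-pass difference, or an odds ratio per SD, with 95% CI, and a small-sample correction when fails are few.
- For categorical characteristics, give an effect estimate with 95% CI alongside the Chi-square test.
- Label all of these results exploratory and put the emphasis on the overall population.
- Reconcile 14.4 with the regression in the protocol summary: either describe it in 14.4 with its outcome, or remove it from the summary.
- If oral steroid dose proves to be mostly zero, also report it as any versus none.

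The cost is a few sentences and minor programming, with no new data, visits or patients. The downside is more exploratory comparisons to report, and subgroup intervals that will be wide.

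### Section 14.4 tests age in single years as an unordered category by chi-square, which leaves almost no power to show an age effect in 140 patients

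*Protocol*

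**What the plan says.** The statistical analysis part of Section 14.4 relates patient characteristics to "pass or fail rates for each of the three test criteria (dependent variables". It divides the characteristics by type. For one type, "box-plots will be used for continuous variables (for example weight and length". For the other, "whereas the Chi-square test will be used for categorical variables (for example diagnosis, age expressed in years, GOLD stage and GOLD group". Age in years stands in the second list, beside diagnosis and GOLD classification, and no age bands are defined for this analysis.

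Section 7.2 sets the matching secondary objective: "To correlate the fail rates for each objective measurement separately with patient's characteristics per patient subgroup and overall". Age is the first characteristic in the list that follows. Section 5.4 gives the reason for interest in age: "The strongest associations have been found between incorrect inhaler technique and older age".

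The protocol summary in Section 1 plans "40 COPD patients (GOLD II-IV); 20 patients with severe asthma", and "40 patients with asthma aged ≥ 70 y, 40 patients with mild-to moderate asthma aged < 70 y". The only general age limit is the exclusion in Section 9.3 of "Patients younger than 18y"; no upper limit is given.

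**The concern.** A chi-square test on age in single years gives each year its own row in a table against pass or fail. Two things go wrong.

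- **Sparse cells.** There are only two or three patients per row, so the expected counts are far too small for the chi-square reference distribution.
- **Lost order.** The test treats ages 71 and 72 as no more alike than 25 and 85. A steady rise in failure with age is spread over more than 50 degrees of freedom instead of one.

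The first problem could be met with an exact or permutation p-value. The second could not, because it comes from the coding of age.

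At stake is the secondary objective on fail rates, for the characteristic that the protocol's own rationale stresses and that it uses, at 70 years, to define the asthma groups. A non-significant result from this test would say almost nothing about age, yet it would probably be read as no association and carried into the larger studies that Section 14.4 foresees.

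**Working it through.** The protocol gives no power, significance level or expected fail rate, so there is no figure of its own to reproduce.

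**Inputs from the protocol**
- Patients (Section 1): 40 + 20 + 40 + 40 = 140.
- Minimum age 18 (Section 9.3); asthma groups split at 70 (Section 9.2).
- Outcome: pass or fail on each of three tests (Section 14.4).

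**Assumptions, not in the protocol**
- Ages in whole years, drawn in two ways. (a) Uniform: COPD 45–85, asthma under 70 at 18–69, older asthma 70–90. (b) Truncated normal: COPD mean 67, SD 8; severe asthma 52, SD 12; older asthma 76, SD 4.5; mild-to-moderate asthma 48, SD 13.
- Overall fail rate 20% or 30%.
- Log-odds of failure linear in age.
- Two-sided 5% level.

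**Step 1: size of the table.** The mean number of distinct ages is 60 under (a), 95% range 55–65, and 52 under (b), 95% range 47–57. Patients per row: 140/60 = 2.3 and 140/52 = 2.7. Degrees of freedom (rows minus 1): about 59 and 51.

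**Step 2: expected counts.** The expected number of fails in a row is the row size times the fail rate. At 20% this is 2.3 × 0.2 = 0.46 to 2.7 × 0.2 = 0.54. An expected count of 5 fails would need 5/0.2 = 25 patients of the same age; an expected count of 5 passes would need 5/0.8 = 6.25, so 7 patients of the same age. In the simulated tables 98–99.8% of cells had an expected count below 5, and 50–64% were below 1.

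**Step 3: power.** Simulation with 2,000 runs per scenario (300 for the permutation p-value). Each range covers the two age distributions and the two fail rates.

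| Odds ratio per 10 years | Chi-square by year | Same statistic, permutation p | 1-df trend | Split at 70 |
|---|---|---|---|---|
| 1.0 (no effect) | 0.9–2.8% | 4–5% | 4.9–5.6% | 4.5–5.4% |
| 1.3 | 1–2% | 4–8% | 40–75% | 30–58% |
| 1.5 | 2–4% | 4–12% | 73–98% | 56–89% |
| 1.75 | 4–13% | 8–33% | 92–99.8% | 80–99% |
| 2.0 | 6–23% | 11–51% | 98–100% | 92–100% |
| 2.5 | 12–53% | 19–74% | about 100% | 98–100% |

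The Mann-Whitney test gave nearly the same power as the trend test.

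The first row shows that the approximation fails: the test rejects in 0.9–2.8% of null samples instead of 5%. The permutation column restores the error rate but recovers only part of the power. The rest is lost because the order of age is ignored.

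**Step 4: a second set of ages.** A separate simulation used COPD mean 67, SD 9; severe asthma 52, SD 12, capped at 69; older asthma 70 plus an exponential with mean 6; mild-to-moderate asthma 46, SD 14, capped at 69; and a 20% fail rate at age 60. It gave about 54 distinct ages. Chi-square power was 2% at an odds ratio of 1.5 and 8% at 2.0, against 84% and 99.8% for logistic regression on continuous age.

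**Step 5: tables within subgroups.** In 20 severe-asthma patients a 20% fail rate gives 20 × 0.2 = 4 expected fails in total, so every fail cell is below 5 however the patients are divided. This holds for any fail rate below 5/20 = 25%. In 40 COPD patients it gives 40 × 0.2 = 8 expected fails, an average of 2 for each of the four GOLD groups.

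**The case against.** Four points can be made for the plan.

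1. **Age is partly tested elsewhere.** Section 14.4 also compares fail rates between patient subgroups, and two of these are asthma aged 70 or over and mild-to-moderate asthma under 70. Under the ages of step 4, this two-group contrast has power of 28%, 55% and 93% at odds ratios of 1.3, 1.5 and 2.0 per 10 years; the four-group table has 44% at 1.5 and 90% at 2.0. So a strong age effect could well show there. This stands, but the contrast mixes age with severity, since the older group includes any severity, and it gives no analysis of age within a subgroup, which Section 7.2 requires.
2. **The summary names multiple regression.** That regression concerns inability to use the device classes, not the three tests. It does not say that age is a covariate, and Section 14.4 does not carry it forward. It does not replace the stated rule, though the two places should be reconciled.
3. **The study is exploratory.** The primary objective is descriptive, no decision depends on this test, and age is recorded for every patient, so nothing is lost for good. This lowers the urgency. It does not make the test suitable.
4. **The figures rest on assumptions.** Section 5.4 cites errors of technique in general, and the size of any age effect on these three tests is unknown. This is fair, and it is why ranges are shown. At an odds ratio of 2.5 the chi-square test reaches 12–53%, so almost no power describes the range 1.3 to 1.75 (1–13%).

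It is also true that the four-group table need not change. At a 20% fail rate only the severe-asthma fail count (4) is below 5, which is 1 of 8 cells. The need for exact tests concerns tables within subgroups.

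**Conclusion.** The concern holds. As written, Section 14.4 assigns age to a test whose approximation is invalid at this sample size and which discards the order of age. For an odds ratio of 1.5 per 10 years the power is 2–4%, against 73–98% when age is kept as a scale; at 2.0 it is 6–23% against 98–100%. The exact figures depend on the assumed ages, fail rates and effect sizes, but the gap is wide under every set tried. If age bands were intended, the text does not say so and still needs correcting.

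The effect is confined to one characteristic in a secondary, exploratory analysis; the prevalence of mismatch is untouched. The wording should be corrected before the analysis, but it is no obstacle to running the study.

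**What to change.** - Take age out of the chi-square list in Section 14.4. For each of the three tests, fit a logistic regression of pass/fail on continuous age and report the odds ratio per 10 years with its 95% confidence interval, overall and by subgroup. Keep box-plots for display. Moving age to the box-plot list alone would give a picture but no estimate.
- Where a subgroup has very few fails, a Mann-Whitney comparison of age between those who pass and those who fail is a workable substitute, with the low precision stated.
- If a categorical view of age is wanted, fix the bands in advance. A split at 70 is already used for the groups and is far better than single years, though weaker than continuous age.
- For sparse tables within subgroups, such as GOLD group in the 40 COPD patients or any table in the 20 severe-asthma patients, use Fisher's exact test or its Freeman-Halton extension.
- Bring Section 14.4 into line with the multiple regression named in the protocol summary.

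The cost is a sentence or two of analysis text. No further patients, visits or data are needed.
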